Depression is a common psychiatric comorbidity with a lifetime prevalence of 16.6% in the United States [25]. Adults with DS have a four- to five-times increased risk of developing depression compared to the general population [13], suggesting that up to 70% of individuals with DS may experience depression in their lifetime. Compared to other known comorbidities associated with DS such as obstructive sleep apnea, congenital heart defects, blood cancers, and cataracts, depression is both relatively more highly prevalent and understudied. No reports on the use of modern antidepressants in DS have been published in the past more than 25 years. Our knowledge of the safety and efficacy of antidepressants in the general population may not be applicable to patients with DS because of the associated medical comorbidities and neurocognitive differences.

The central hypothesis of this project is that adults with major depression and DS will experience an improvement in depressive symptoms after a course of fluoxetine treatment. We also expect that fluoxetine will be safe and well tolerated. This study will provide much needed preliminary prospective

data regarding the effectiveness and tolerability of fluoxetine for these symptoms in DS and is a necessary first step prior to conducting a larger, more definitive placebo-controlled trial.

2. Specific Aims and Objectives

Specific Aim 1: Determine whether a 16-week prospective, open-label trial of fluoxetine shows preliminary evidence of effectiveness, safety, and tolerability in adults with DS and major depressive disorder (MDD).

This aim addresses our central hypothesis that fluoxetine will be effective and safe in the treatment of depression in adults with DS.

- A)** For preliminary evidence of effectiveness, we will require an observed response rate (where response is defined as a 16-week CGI-I rating of “much improved” or “very much improved”) of 35% or greater. We will use the CGI-I rather than a depression scale for our effectiveness criterion because of the absence of existing data supporting the usefulness of common scales for quantifying depression severity in adults with DS.
- B)** For preliminary evidence of safety, we will require no observation of serious or severe adverse effects possibly, probably, or definitely associated with fluoxetine.
- C)** For preliminary evidence of tolerability, we will require an observed drop-out rate due to adverse effects less than 36%.

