#Screen and Baseline Visits may be combined into a single visit if subject clearly meets eligibility criteria.
^Telephone Visit; ^^In clinic; ^^^In clinic, Zoom, or telephone; **Administered when emotional regulation, cognitive, and communicative abilities allow; [1] Parent or primary caretaker ratings; [2] SCID-5 = Structured Clinical Interview for DSM-5; [3] MADRS = Montgomery-Asberg Depression Rating Scale; [4] HAM-D = Hamilton Depression Rating Scale; [5] GDS-CS = Glasgow Depression Scale for people with a Learning Disability Carer Supplement; [6] PSQI = Pittsburgh Sleep Quality Index; [7] Females of child-bearing potential only; [8] genetic testing or clinical diagnosis; [9] CGI-S = Clinical Global Impression for Severity; [10] CGI-I = Clinical Global Impression for Improvement; [11] Suicide Assessment included in Adverse Effect Review; [12] Columbia-Suicide Severity Rating Scale (C-SSRS) will only be administered to participant and/or parent if any positive suicidal ideation is reported on Health/Behavior Review (screen) or Adverse Effects Review (baseline and all subsequent visits). Each visit following the first report of suicidal ideation will include the administration of the C-SSRS.

Drug Compliance

Families will be asked to return drug diaries within 5 business days of the scheduled Week 2, 4, 6, 8, 10, 12, and 16 visits. The study coordinator and/or PI will calculate drug compliance based on the number of missed doses between visits. Adequate compliance will be defined as $\geq 70\%$ of doses. If compliance falls

below this threshold and/or drug diaries are not returned, the subject may be discontinued from the study, per PI discretion.

7. Risks and Discomforts

Overall, the risk to the subjects in this research are essentially no different from those that would exist in standard clinical practice, but the research proposed offers considerable promise in improving our understanding of the treatment of depression in individuals with Down syndrome. Foreseeable risks and discomforts include:

Drug-free washout interval

Withdrawal of a medication prior to the study will only be pursued in cases for which the current medication is not effective or is causing intolerable side effects. In collaboration with the prescribing clinician, the medication will be gradually tapered according to best clinical practices with close monitoring for symptom worsening.

Fluoxetine Treatment

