A meta-analysis investigating the effectiveness of fluoxetine treatment estimated the intent-to-treat probability of response to treatment as measured using the CGI-I to be 44% [32]. In addition, the lower bound of the 95% confidence interval for response to treatment from our retrospective study excluded values less than or equal to 50%. A sample size of 20 provides a greater than 90% chance of observing a response rate of 35% or greater if the population probability of response is 44% or greater and a greater than 90% chance of observing a response rate less than 35% if the true probability of response is 20% or less. For safety outcomes, if there is a serious or severe adverse event associated with fluoxetine treatment in the population of adults with DS that occurs with a frequency of 10% or greater, we will have an 85% or greater chance of observing it in the study and concluding there are safety concerns with fluoxetine use for depression in adults with DS, assuming at least 90% (n=18) of participants remain in the study long enough to experience the event. For tolerability, assuming at least 85% of patients complete treatment or withdraw due to adverse effects, a sample size of 20 provides greater than 90% chance of observing a dropout rate due to side effects less than 36%, assuming at least 80% of adults with DS and depression in the population can tolerate a 16 week treatment course, and at least an 80% chance of observing a dropout rate due to side effects of 36% or greater assuming no more than 50% of adults with DS can tolerate a 16 week treatment course. Assuming an overall completion rate of 70%, a sample size of 20 also allows estimation of mean changes in depression scale score and mean dosage at study completion with a 95% confidence interval half width of 0.6 standard deviations, assuming a correlation of 0.5 between baseline and week 16 measurements.

Statistical Analysis Plan:

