We will estimate percentage response to fluoxetine treatment, and corresponding 95% confidence interval, for adults with DS using the proportion of participants with CGI-I scores ≤ 2 at 16 weeks. Participants with missing 16-week CGI-I scores will be treated as non-responders. Frequency of all side effects and adverse events and corresponding 95% confidence intervals will be tabulated. Percent tolerating treatment and corresponding 95% confidence intervals will be estimated using the proportion of participants who did not withdraw from the study before 16 weeks due to reasons other than side effects or an adverse event who discontinue treatment due to side effects or an adverse event. We will also use the 16-week study retention rate and corresponding 95% confidence interval, calculated as the proportion of the participants enrolling in the study who remain in the study for 16 weeks, as a measure of feasibility.

To estimate changes in depression scale scores, including the MADRS, HAM-D, GDS-LD, and GDS-CS, we will use repeated measures linear regression models, as implemented in PROC MIXED in SAS and fit using REML estimation, with repeated measurements of clinical scores as outcomes and time, in categories, as the predictor. We will allow unstructured covariance between repeated measurements from the same participant. Our primary interest will be only in the difference between baseline and week 16 scores, but all observed scores will be included as outcomes, given that partially observed scores may be informative for estimation. We will obtain an estimate of 16-week change and corresponding 95% confidence interval using a contrast of the week 16 and baseline model parameters. Sensitivity to change will be compared between scales using standardized effect sizes, calculated using the model-estimated 16-week change in each outcome divided by 1) the model-estimated standard deviation of the outcome at baseline and 2) the model-estimated standard deviation of the change score. Spearman correlations will quantify the strength of association between change in depression scale score and CGI-I ratings among those with observed 16-week data. We will also tabulate and compare the percent of item-level missing data for each scale.

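### Low compliance or an unreturned drug diary can end study follow-up at the PI's discretion, creating avoidable missing week-16 outcomes and leaving the tolerability count dependent on how the exit is coded

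*Combined protocol and SAP*

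**What the plan says.** Section 6 (Drug Compliance) asks for diaries around each visit from week 2 to week 16. "The study coordinator and/or PI will calculate drug compliance based on the number of missed doses between visits", and 70% of doses is the adequacy threshold. If compliance falls "below this threshold and/or drug diaries are not returned, the subject may be discontinued from the study, per PI discretion". No criteria guide that discretion. The documents describe no early-termination visit and no assessment after such a removal.

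Two rules in Section 9 (Statistical Analysis Plan) then apply:

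- Primary endpoint: "Participants with missing 16-week CGI-I scores will be treated as non-responders".
- Tolerability: the proportion is taken among "participants who did not withdraw from the study before 16 weeks due to reasons other than side effects or an adverse event".

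The decision limits are in Section 2, Specific Aim 1. Effectiveness needs an observed response rate "of 35% or greater". Tolerability needs a drop-out rate from adverse effects below 36%.

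The trial is open-label (Section 3). Table 1 has the treating clinician rate CGI-I at weeks 4, 8, 12 and 16.

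**The concern.** A missed-dose count or a late diary says nothing directly about whether the participant improved. Yet it can end outcome collection for someone who could still be rated. The decision is made case by case, without blinding, when earlier CGI-I ratings may already be known.

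One removal before week 16 feeds two Aim 1 rules. For 1A, an obtainable rating is replaced by an assumed failure. For 1C, the result depends on how the exit is labelled. Side effects can cause missed doses, and the plan does not say whether such an exit counts as a side-effect discontinuation or as non-compliance. The first label keeps the participant in numerator and denominator; the second removes the participant from both.

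Removal also lowers the 16-week retention rate, loses the week-16 scale scores for Aim 2, and takes the participant out of the completer-only mean dose for Aim 3.

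**Working it through.** **Inputs.** From Section 9 (Sample Size Considerations): n = 20; response 44% (favourable) and 20% (unfavourable); at least 85% completing or withdrawing for adverse effects, so 0.85 × 20 = 17 evaluable for tolerability; true tolerability 80% (good) or 50% (poor). From Section 2: response at or above 35%, so 7 of 20; adverse-effect drop-out below 36%. The documents give no non-compliance rate, so the removal counts are assumptions. Three is the largest number compatible with the plan's own 85%, since 20 − 17 = 3 leave for all other reasons combined.

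**Plan's own figures (exact binomial).**

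- P(X ≥ 7 | 20, 0.44) = 85.0%. The plan states more than 90%; this does not reproduce. That is a separate matter, and 85.0% is the starting point here.
- P(X < 7 | 20, 0.20) = 91.3%; reproduces the stated figure of more than 90%.
- With 17 evaluable, at most 6 drop-outs pass (6/17 = 35.3%). P(pass | 20% drop-out) = 96.2% and P(fail | 50% drop-out) = 83.4%; both reproduce (more than 90%, at least 80%).

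**Response, k participants removed before the week-16 rating.** The denominator stays at 20 and only 20 − k can be responders. If those removed would have responded at 44%, the chance of meeting the rule is P(X ≥ 7 | 20 − k, 0.44):

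| k | Chance of meeting the rule | Expected observed rate |
|---|---|---|
| 0 | 85.0% | 44.0% |
| 1 | 80.4% | 41.8% |
| 2 | 74.8% | 39.6% |
| 3 | 68.0% | 0.44 × 17/20 = 37.4% |

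Poor adherers may respond less often. Hold the overall rate at 44% (8.8 expected responders in 20) and let the three respond at rate q. The other 17 then respond at (8.8 − 3q)/17:

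- q = 20%: (8.8 − 0.6)/17 = 48.2%. The chance is 85.5% if all 20 are rated and 79.5% if the three are removed.
- q = 10%: (8.8 − 0.3)/17 = 50.0%. The chance is 86.1% if all are rated and 83.4% if the three are removed.

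At a true rate of 20%, three removals lower the false-positive chance P(X ≥ 7) from 8.7% to 3.8%.

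Section 4 plans 25 adults, not 20. With 25, 9 responders are needed, and the chance at 44% goes from 84.3% to 69.1% with three removals: much the same picture.

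**Tolerability, limit below 36%.**

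- Side-effect exits coded as non-compliance: 8/20 = 40.0% (fails); two recoded gives 6/18 = 33.3% (passes). With the plan's 17 evaluable: 7/17 = 41.2% (fails); 5/15 = 33.3% (passes).
- Removal of one participant without a side-effect stop: 7/20 = 35.0% (passes); 7/19 = 36.8% (fails). With 17: 6/17 = 35.3% (passes); 6/16 = 37.5% (fails).
- Not every recoding crosses the limit: 8/20 with one recoded gives 7/19 = 36.8%, and 9/20 with two recoded gives 7/18 = 38.9%. Both still fail.
- With 17 evaluable and a true adverse-effect drop-out of 50%, the chance of wrongly passing is 16.6% with no recoding, and 19.6%, 27.0% or 36.9% if 10%, 20% or 30% of side-effect exits are recoded (assumed shares).

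**The case against.** The strongest defence is that the primary analysis is already protected. Missing counts as failure, so discretionary removal cannot raise the responder count. A reader might infer that the PI could use the rule to improve the response result; the documents do not support that. This part stands. But imputation is meant for missing data that cannot be avoided, and here the protocol creates it. Imputation also does nothing for tolerability or retention.

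A reader might also infer that the rule always flatters tolerability. It does not. That direction needs side-effect exits to be coded as non-compliance, and this is a possibility, not a demonstrated outcome. Adverse effects are reviewed at every treatment-phase contact, and the physician's log records whether an event changed the study intervention (Section 6, Safety Monitoring). An exit attributed to side effects is counted correctly. What remains is narrower: no rule covers non-compliance that side effects caused.

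The 68% should not be read as the expected loss. It takes three removals and the full 44% response among people missing more than 30% of doses. The plan also describes 44% as an intent-to-treat figure, so subtracting removals from it may count some attrition twice.

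Nor are the scale data lost altogether. The repeated-measures model keeps all observed scores, so earlier visits contribute; the week-16 value is what goes missing. A participant flagged only by the week-16 diary may already have been rated.

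Finally, the rule says that a participant may be discontinued, so retention is already permitted. That limits the size of the problem but leaves the handling unspecified.

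**Conclusion.** The point holds as a design weakness that is cheap to remove. A stated rule can turn ratable participants into assumed non-responders and can make the tolerability result depend on an undefined coding choice.

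For response, the bias is conservative: with three of 20 removed, the loss is from 85% to 68% if they would have responded at the overall 44%, and from about 86% to 80-83% if at 10-20%. For tolerability, the direction is not fixed, and one or two participants near the 36% limit can change the result either way.

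These sizes rest on assumed numbers removed, on removal before the week-16 CGI-I, and on PI-initiated exits for non-compliance being treated as withdrawals for a reason other than side effects. The actual effect depends on how often the discretion is used. If it is never used, there is none.

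**What to change.** Reword the Drug Compliance paragraph so that low compliance or missing diaries do not end study follow-up. Unless consent or assent is withdrawn, these participants complete the scheduled week-16 CGI-I, depression scales and adverse-effect review, and are analysed as observed. Whether drug continues stays with the existing clinical judgement.

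In Section 9, add a classification rule for Aim 1C. A participant who actually stops fluoxetine is classified by the recorded reason, so a stop due to side effects counts as a side-effect discontinuation even if it first appears as missed doses. Missed doses alone, in someone who continues treatment, are not a drop-out; counting them would contradict the Aim 1C definition.

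The cost is a short amendment to two sections and some effort to complete visits that are already scheduled and that Table 1 allows by Zoom or telephone. The downside is that the response estimate will include poorly adherent participants.

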2. **Current or previous diagnosis of dementia, or use of medication to treat dementia.** Given the potential overlap between depression and dementia symptoms, we want to ensure we are administering fluoxetine to patients with a diagnosis of depression.

3. **Presence of any past or present conditions that would make treatment with fluoxetine unsafe.** This includes allergy to fluoxetine, liver or kidney disease, unstable heart disease, and/or pregnancy (or being sexually active without using acceptable methods to prevent pregnancy).
4. **Use of selective serotonin reuptake inhibitors (SSRIs), serotonin norepinephrine reuptake inhibitors (SNRIs), tricyclic antidepressants (TCAs), monoamine oxidase inhibitors (MAOIs), bupropion, mirtazapine, antipsychotics, lithium, valproic acid, or carbamazepine.** Subjects will need to be off these classes of medications for at least 5 elimination half-lives prior to beginning the trial.
5. **Use of other psychotropic medications which are ineffective, poorly tolerated, or sub-optimal in terms of dose.** A board-certified psychiatrist will assess any other psychotropic medications being used and determine whether they are effective, tolerated, and optimal in terms of dose. If medications are ineffective, poorly tolerated, or sub-optimal in terms of dose, the study psychiatrist will work with the subject and his/her treatment team to either taper or optimize the dose of psychotropic medications prior to study enrollment. Concurrent use of a psychotropic medication (other than SSRIs, SNRIs, TCAs, MAOIs, bupropion, mirtazapine, antipsychotics, lithium, valproic acid, or carbamazepine) will be allowed if the dose has been stable for 30 days and if they meet the criteria of effectiveness, tolerability, and dose.
6. **Previous adequate trial of fluoxetine.** An adequate trial will be defined as a total daily dose of ≥ 30 mg for at least 4 weeks. In addition, subjects who developed significant adverse effects during a trial of fluoxetine at any dose or duration will be excluded.
7. **Severe or profound intellectual disability based on clinical assessment and review of standardized assessment of cognitive skills.** Participants determined to have severe or profound intellectual disability will be excluded.
8. **Use of medications that pose a clinically significant risk of a drug-drug interaction with fluoxetine.**

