Fluoxetine Treatment:

Subjects will receive fluoxetine 5 mg each morning at the start of the trial. The dose will be flexibly increased by 5 mg every two weeks depending on effectiveness and tolerability. During the first 12 weeks, patients will be seen monthly with additional telephone visits conducted in between clinical visits for additional monitoring of adverse effects and for dosing adjustment as necessary. The optimal dose (between 5-30 mg per day), based on effectiveness and tolerability, will be reached by week 12 of treatment. A final visit will be conducted at week 16. At the end of the 16-week trial, participants will be referred for ongoing care either at the Lurie Center or locally, per their preference. The decision to continue or discontinue fluoxetine at the end of the trial will be made collectively by the research psychiatrist, the patient, and their family.

The minimum starting dose will be 5 mg and the maximum total daily dose will be 30 mg. If up titration is not tolerated, no more than one repeat attempt at up titration will be made. The decision to attempt a repeat up titration will be made by the research psychiatrist taking into account the full clinical picture of probable risks and benefits as well as the patient/family's preference. Fluoxetine is prepared in 10 mg tablets as well as a liquid formulation and will be dosed daily (see example of dosing schedule below).

Example Dosing Schedule	
	Dose (mg)
Weeks 1 & 2	5
Weeks 3 & 4	10
Weeks 5 & 6	15
Weeks 7 & 8	20
Weeks 9 & 10	25
Weeks 11 & 12	30

Weeks 13-16	Stable dose for last 4 weeks of study
* The schedule is a guide and may be adjusted depending on tolerability and effectiveness.	

The rationale for this dosing schedule is based upon pilot data our group obtained. A retrospective chart review study from our clinic included 11 adults with DS and depression who were treated with a selective serotonin reuptake inhibitor (most commonly fluoxetine). The overall response rate was 82%. The mean starting dose for fluoxetine was 4.9 mg per day and the mean maximal dose was 25.5 mg per day. [20]

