Participants will be monitored for possible pregnancy throughout the study. If a participant is of childbearing potential, a urine pregnancy test will be obtained at Screen. A positive result on a urine pregnancy test will then be confirmed via a blood pregnancy test, and a positive result on a blood pregnancy test will exclude them from study participation. We will continue to assess for pregnancy at all monthly clinic visits by asking participants if they are sexually active and if they are using contraception. Participants of childbearing potential who are sexually active and are not using an approved contraception method will be asked to complete a urine pregnancy test. A positive result on a urine pregnancy test will then be confirmed via a blood pregnancy test, and a positive result on a blood pregnancy test will exclude them from study participation.

Adverse events will be collected via a structured side effect rating scale completed with the participant and their primary caregiver. This will include a list of side-effects that have been reported with fluoxetine at a rate greater than 10% including sexual dysfunction, anorexia, diarrhea, nausea, dry mouth, anxiety, drowsiness, headache, insomnia, yawning, asthenia, tremor, and pharyngitis. Each of these side effects plus any additional complaints will be rated at baseline on a 4-point scale by the caregiver as follows: 0 = none; 1 = mild; 2 = moderate; 3 = severe. This scale is similar to that used by the RUPP Autism Network. Suicidality will be assessed at each visit by directly asking the subject (when verbal skills are sufficient) and the caregiver about any thoughts or behaviors that directly or indirectly might indicate suicidality (e.g., morbid thoughts, self-injury, statements about life being not worth living), when indicated by positive responses. At baseline, if suicidality is endorsed, the Columbia-Suicide Severity Rating Scale (C-SSRS) will be administered per the instructions at www.cssrs.columbia/ed/clinical_trials.html. The C-SSRS will also be administered at each subsequent visit following the first report of suicidality. Subjects and caregivers will also have information on how to contact the on-call physician from our practice group who provides coverage 24 hours/day and 365 days/year. Physicians taking call are familiar with research protocols and can contact the principal investigator at any time.

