Fluoxetine, an SSRI, has been well tolerated in children, adolescents, and adults. Common adverse reactions (>10%) include, asthenia, nausea, diarrhea, insomnia, nervousness, anxiety, and somnolence. Less common adverse reactions (<10%) include flu symptoms, decreased appetite, dry mouth, dyspepsia, constipation, dizziness, tremor, sweating, fever, vasodilation, flatulence, vomiting, weight loss, decreased libido, abnormal thinking, yawning, rash, pruritis, and abnormal vision. Very rarely, SSRIs may increase the risk of bleeding, a mixed/manic mood episode, suicidal thoughts, and/or QT prolongation. There is also the rare but potential risk of serotonin syndrome. If discontinued abruptly, fluoxetine discontinuation syndrome including flu-like symptoms, insomnia, nausea, balance problems, sensory disturbances, and hyperarousal may occur.

We will assess for these symptoms at all phone, video, and in-person visits. Any side effects will be closely monitored and recorded. In order to manage a side effect or suspected adverse event, the treating clinician is free to delay a scheduled increase or reduce the dose of the study medication. The dose schedules described above are guides only.

Fluoxetine has a half-life of 4 to 6 days. No specific laboratory monitoring is recommended with fluoxetine treatment.

Allergic Reactions

An allergic reaction can occur. Allergic reactions can be mild or serious and can even result in death. Common symptoms of an allergic reaction are rash, itching, skin problems, swelling of the face and throat, or trouble breathing. Participants will be instructed to call the study doctor immediately if they suspect they are having an allergic reaction. Participants will also be instructed to call 911 immediately and get medical assistance if they are having trouble breathing.

Risks to an Embryo or Fetus, or to a Breastfeeding Infant

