Fluoxetine and its metabolite cross the placenta and are also present in breast milk. The effect of fluoxetine on an embryo or fetus, or on a breastfeeding infant, can be harmful. Due to these risks, individuals cannot take part in this study if they are pregnant, trying to become pregnant or breastfeeding. If a potential female participant is of childbearing age, a urine pregnancy test will be obtained at Screen, and a positive result will exclude them from study participation. Potential participants who are sexually active or able to become pregnant will be required to agree to use an approved birth control method for the entire study and for at least two weeks after the last dose of study drug. Acceptable birth control methods for use in this study are abstinence, condoms, or birth control pills.

Suicide Risk

Suicidality will be assessed at each visit by directly asking the subject (when verbal skills are sufficient) and caregiver about any thoughts or behaviors that directly or indirectly might indicate suicidality (e.g., morbid thoughts, self-injury, statements about life not being worth living). The baseline C-SSRS for any subject who endorses suicidality will be done per the instructions at www.cssrs.columbia.edu/clinical_trials.html. The C-SSRS will also be administered at each subsequent visit following the first report of suicidality. If the subject answers "Yes" to Question 4 or 5 on the C-SSRS, the study physician will be notified immediately, and the subject will be emergently evaluated by a licensed study clinician for appropriate assessment and triage. Subjects who develop significant suicidal ideation (plan, gesture, attempt) will be treated and removed from the study if indicated.

Health Assessments, Behavioral Assessments and Checklists

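### Two weeks of contraception after the last dose is only 2.3 to 3.5 half-lives at the protocol's own figure; the minimum should be at least 30 days

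*Combined protocol and SAP*

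**What the plan says.** The rule is in Section 7, under Risks to an Embryo or Fetus, or to a Breastfeeding Infant. Potential participants who are sexually active or able to become pregnant must agree to approved birth control "for the entire study and for at least two weeks after the last dose of study drug". The reason precedes it: "Fluoxetine and its metabolite cross the placenta and are also present in breast milk", and "The effect of fluoxetine on an embryo or fetus, or on a breastfeeding infant, can be harmful".

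Earlier in Section 7, under Fluoxetine Treatment, the protocol states: "Fluoxetine has a half-life of 4 to 6 days". It gives no half-life for the metabolite.

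On follow-up, Section 6 (Safety Monitoring) says "We will continue to assess for pregnancy at all monthly clinic visits", and Table 1 places these assessments at Weeks 4, 8, 12 and 16. Section 6 (Fluoxetine Treatment) adds "A final visit will be conducted at week 16". "The decision to continue or discontinue fluoxetine at the end of the trial" is left to the research psychiatrist, the patient and the family together, with referral for ongoing care.

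One other passage sets a clearance period. Exclusion 4 in Section 4 covers SSRIs and other psychotropic classes: "Subjects will need to be off these classes of medications for at least 5 elimination half-lives prior to beginning the trial".

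**The concern.** The protocol accepts that fetal exposure after the last dose warrants contraception, then sets a period that its own half-life does not support. No basis for two weeks appears anywhere, and no passage requires longer.

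The issue is participant safety. Someone who follows the rule literally may stop contraception while a measurable share of the drug is still present. With the last visit and last pregnancy assessment at Week 16, no planned study contact would detect a pregnancy after that. For a participant who stops fluoxetine then, the contraception period is the only fetal protection the protocol requires. Stopping is foreseen: continuation is decided individually at Week 16, and the sample size section allows for a completion rate of 70%.

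**Working it through.** The two-week figure has no stated derivation, so there is nothing to reproduce. It can only be tested against the protocol's half-life.

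**Inputs**
- Contraception period after the last dose: 14 days (Section 7).
- Fluoxetine half-life, t½: 4 to 6 days (Section 7); 5 days is used as the midpoint.
- Benchmark by analogy: 5 half-lives (Exclusion 4, a washout rule).

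**Formulas** (first-order elimination assumed)
- Half-lives elapsed = days / t½
- Fraction remaining = 0.5^(days / t½), relative to the level at the last dose
- Days needed for k half-lives = k × t½

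**Results for the parent drug**

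| t½ (days) | Half-lives in 14 days | Remaining at day 14 | Days for 5 half-lives | Half-lives in 30 days | Remaining at day 30 |
|---|---|---|---|---|---|
| 4 | 14/4 = 3.5 | 8.8% | 20 | 7.5 | 0.6% |
| 5 | 14/5 = 2.8 | 14.4% | 25 | 6.0 | 1.6% |
| 6 | 14/6 = 2.33 | 19.8% | 30 | 5.0 | 3.1% |

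Against five half-lives, two weeks is short by 20 − 14 = 6 days to 30 − 14 = 16 days. Five half-lives leave 0.5^5 = 3.1%. The day-14 residual is 0.088/0.03125 = 2.8 to 0.198/0.03125 = 6.3 times that.

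**Does the result depend on choosing five?**
- Four half-lives take 16 to 24 days, so 14 days falls short across the whole stated range.
- Three half-lives take 12 to 18 days, so 14 days is enough only if t½ is at most 14/3 = 4.7 days.
- For 14 days to equal five half-lives, t½ would have to be 14/5 = 2.8 days, below the stated range.

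**Metabolite.** The documents give no half-life, so these values are assumptions that show only the direction of the effect.

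| Assumed t½ (days) | Remaining at day 14 | Remaining at day 30 | Days for 5 half-lives |
|---|---|---|---|
| 7 | 25.0% | 5.1% | 35 |
| 10 | 37.9% | 12.5% | 50 |
| 14 | 50.0% | 22.6% | 70 |

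A period that must cover both compounds cannot be shorter than the one for the parent drug, so 30 days is a floor.

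**The case against.** The strongest reply is that the five-half-life standard is borrowed. Exclusion 4 concerns washout of prior drugs, and nothing in the protocol sets a clearance criterion for contraception. The documents also give no exposure level at which fetal risk ends. Both points stand. The two passages do not contradict each other, and harm at two weeks has not been shown. But the shortfall does not rest on that benchmark alone, because two weeks also misses four half-lives throughout the stated range.

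Second, 30 days is derived from the parent drug, so the documents cannot show that it is adequate for the metabolite. This is correct, but it argues for a longer period and not for keeping two weeks.

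Third, the percentages are relative to the level at the last dose. A participant stepped down before stopping would have a lower absolute residual. That is fair, but the protocol specifies no taper at the end of the trial.

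Fourth, the wording sets a minimum, and the handover to ongoing care gives an opportunity for individual advice. Neither requires longer contraception, and the handover text does not mention pregnancy.

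Finally, the group at risk is very small. Of 25 planned participants, it is those able to become pregnant who stop fluoxetine and then stop contraception, and it may be empty. Exclusion 3 already removes those who are sexually active without acceptable contraception, and those who continue fluoxetine after Week 16 are outside this window. This limits the expected number of events but not the seriousness of one.

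**Conclusion.** The concern holds. At the protocol's stated half-life, the contraception requirement can lapse with 8.8% to 19.8% of the parent drug remaining, 6 to 16 days before five half-lives have passed, with no stated reason and no later pregnancy assessment. The figures assume first-order elimination and leave the metabolite out. Five half-lives is a reasonable benchmark taken by analogy, not a rule the protocol has broken. The conclusion is that the period is unsupported and too short by the protocol's own figures, not that harm would follow. It is a safety correction worth making and has no bearing on the trial's statistical conclusions.

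**What to change.** In Section 7, replace the two-week minimum with at least 30 days after the last dose, or longer if the clinical team's figure for the metabolite half-life requires it. Add one sentence giving the basis: five half-lives at the 6-day upper value is 5 × 6 = 30 days, with the metabolite considered. Use the same period in the participant information, which was not available for this review. Exclusion 4 needs no change.

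The cost is a wording amendment and about 30 − 14 = 16 more days of contraception for the few participants who can become pregnant and who stop fluoxetine. Visits, sample size and analysis are unaffected.
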